#### 8.1.3 Clinical outcome assessments

A clinical outcome assessment is any assessment that may be influenced by human choices, judgement, or motivation and may support either direct or indirect evidence of treatment benefit. PRO is one type of clinical outcome assessment. PRO is an umbrella term referring to all outcomes and symptoms that are directly reported by the patient. PROs have become a significant endpoint when evaluating the effectiveness of treatments in clinical studies and will aid in understanding of the benefit/risk evaluation. The following PRO instruments will be administered in this study: EORTC QLQ-C30 v3 (core questionnaire), EORTC QLQ-LC13 (lung cancer module), PRO-CTCAE, Patient's Global Impression of Severity (PGIS), and 5-level health state utility index (EQ-5D-5L) (see Appendix H).

## 8.1.3.1 EORTC QLQ-C30 and QLQ-LC13

The EORTC QLQ-C30 was developed by the EORTC Quality of Life Group 1993. It consists of 30 items and measures symptoms, functioning, and global health status/QoL (Aaronson et al 1993) for all cancer types. Questions are grouped into 5 multi-item functional scales (physical, role, emotional, cognitive, and social); 3 multi-item symptom scales (fatigue, pain, and nausea/vomiting); a 2-item global QoL scale; 5 single items assessing additional symptoms commonly reported by cancer patients (dyspnea, loss of appetite, insomnia, constipation, and diarrhea), and 1 item on the financial impact of the disease. The EORTC QLQ-C30 is a valid and reliable PRO instrument in this patient population.

The QLQ-LC13 is a well-validated complementary module measuring lung cancer-associated symptoms and side effects from conventional chemotherapy and radiotherapy (Bergman et al 1994). The QLQ-LC13 includes questions assessing cough, hemoptysis, dyspnea, site-specific pain (symptoms), sore mouth, dysphagia, peripheral neuropathy, alopecia (treatment-related symptoms), and pain medication.

#### **8.1.3.2 PRO-CTCAE**

The PRO-CTCAE will only be administered in countries where a linguistically validated version exists.

PRO-CTCAE was developed by the National Cancer Institute (NCI) in recognition that collecting treatment-related symptom data directly from patients can improve accuracy and efficiency. This was based on findings from multiple studies demonstrating that physicians and nurses underestimate symptom onset, frequency, and severity in comparison with patient ratings (Basch et al 2009, Litwin et al 1998, Sprangers and Aaronson 1992). To date, 81 symptoms of the CTCAE (version 4) have been identified to be amenable to patient reporting, but not all items are administered in any clinical study. Response options vary in frequency, severity, and interference with usual activities. For this study, 9 symptoms are considered relevant for this cancer treatment (see Appendix H).

#### 8.1.3.3 **PGIS**

The PGIS item is included to assess how a patient perceives his/her overall current severity of cancer symptoms. Patients will choose from response options from "no symptoms" to "very severe."

#### 8.1.3.4 EQ-5D-5L

The EuroQoL 5-Dimension (EQ-5D) is a standardized measure of health status developed by the EuroQoL Group in order to provide a simple, generic measure of health for clinical and economic appraisal (EuroQoL Group 1990). Applicable to a wide range of health conditions and treatments, it provides a simple descriptive profile and a single index value for health status that can be used in the clinical and economic evaluation of health care as well as in population health surveys. The questionnaire assesses 5 dimensions as follows: mobility, self-care, usual activities, pain/discomfort, and anxiety/depression. Each dimension has 5 response options ("no problems," "slight problems," "moderate problems," "severe problems," and "extreme problems") that reflect increasing levels of difficulty (EuroQoL Group 2013).

Since 2009, the EuroQol Group has been developing a more sensitive version of the EQ-5D (the EQ-5D-5L) that expands the range of responses to each dimension from 3 to 5 levels of increasing severity (Herdman et al 2011). Preliminary studies indicate that the 5L version improves upon the properties of the 3L measure in terms of reduced ceiling effect, increased reliability, and an improved ability to differentiate between different levels of health (Janssen et al 2008a, Janssen et al 2008b, Pickard et al 2007).

The patient will be asked to indicate his/her current health state by selecting the most appropriate level in each of the 5 dimensions. The questionnaire also includes a visual analog scale, where the patient will be asked to rate current health status on a scale of 0 to 100, with 0 being the worst imaginable health state (see Appendix H).

## 8.1.3.5 Administration of electronic patient-reported outcome questionnaires

Other than at the baseline visit where assessments are completed at site, patients will complete the PRO assessments outside the site by using a handheld electronic device (electronic patient-reported outcome [ePRO]). The following best-practice guidelines should be followed when collecting PRO data via an electronic device:

- Site staff should explain the value and relevance of hearing directly from the patients how they feel. The research nurse or appointed site staff should also stress that the information is confidential. Therefore, if the patient has any medical problems, he/she should discuss them with the doctor or research nurse separately from the ePRO assessment.
- Remind patients that there are no right or wrong answers; avoid bias by not clarifying items.
- Train the patients on how to use the ePRO device using the materials and training provided by the ePRO vendor. Also, provide guidance on whom to call if there are problems with the device by providing the patient information pamphlet provided by the ePRO vendor.
- It is vital that the ePRO reporting is initiated prior to dosing and prior to any other assessments while the patients are still in the clinic on Cycle 1 Day 1, as specified in the study plan, to capture the effect of study treatment.

- If the patient is unable to read (eg, is blind or illiterate), that patient is exempted from completing the ePROs and may still participate in the study. Patients exempted in this regard should be flagged appropriately by the site staff.
- All PRO questionnaires are to be completed using the ePRO device. If the device is not yet at the site or there is a technical problem, the study team may grant use of a paper backup using electronic screenshots for baseline only. Study team approval must be obtained prior to the use of a paper backup using electronic screenshots at baseline. If not, the use of a paper backup will be considered a protocol deviation.

In order to minimize missing data, compliance must be checked frequently to identify problems early. If compliance drops below 90%, a check-in call from the site to ask the patient if he/she has any difficulties is highly recommended.

## 8.2 Safety assessments

Planned time points for all safety assessments are provided in the SoAs (Table 1 and Table 2).

## 8.2.1 Clinical safety laboratory assessments

Blood and urine samples for determination of clinical chemistry, hematology, and urinalysis will be taken at the times indicated in the assessment schedules and as clinically indicated (see the SoAs).

Clinical laboratory safety tests, including serum pregnancy tests, will be performed in a licensed clinical laboratory according to local standard procedures. Sample tubes and sample sizes may vary depending on the laboratory method used and routine practice at the site. Pregnancy tests may be performed at the site using a licensed test (urine or serum pregnancy test). Abnormal clinically significant laboratory results should be repeated as soon as possible (preferably within 24 to 48 hours).

Additional safety samples may be collected if clinically indicated at the discretion of the Investigator. The date, time of collection, and results (values, units, and reference ranges) will be recorded on the appropriate eCRF.

The laboratory variables to be measured are presented in Table 8 (clinical chemistry), Table 9 (hematology), and Table 10 (urinalysis).

Other safety tests to be performed at screening include assessment for hepatitis B surface antigen, hepatitis C antibodies, and HIV antibodies.

The following laboratory variables will be measured:

## Table 8 Clinical chemistry

Albumin	Lipase b
Alkaline phosphatase	Magnesium c
ALT a	Potassium
Amylase b	Sodium
AST a	Total bilirubin a
Bicarbonate c	Total protein
Calcium	TSH d
Chloride c	T3 free e (reflex)
Creatinine	T4 free e (reflex)
Gamma glutamyltransferase c	Urea or blood urea nitrogen, depending on local practice
Glucose	

Lactate dehydrogenase

- Tests for ALT, AST, alkaline phosphatase, and total bilirubin must be conducted and assessed concurrently. If total bilirubin is ≥2 × upper limit of normal (and no evidence of Gilbert's syndrome), then fractionate into direct and indirect bilirubin.
- It is preferable that both amylase and lipase parameters are assessed. For sites where only one of these parameters is routinely measured, either lipase or amylase is acceptable.
- Bicarbonate (where available), chloride, creatinine clearance, gamma glutamyltransferase, and magnesium testing are to be performed at baseline, on Day 1 (unless all screening laboratory clinical chemistry assessments are performed within 3 days prior to Day 1), and if clinically indicated.
- If TSH is measured within 14 days prior to Day 1 (first infusion day), it does not need to be repeated at Day 1.
- Free T3 or free T4 will only be measured if TSH is abnormal or if there is a clinical suspicion of an AE related to the endocrine system.
- AE Adverse event; ALT Alanine aminotransferase; AST Aspartate aminotransferase; TSH Thyroid-stimulating hormone.

#### Table 9 Hematology

Absolute neutrophil count a	Absolute lymphocyte count a
Hemoglobin	Platelet count
Total white cell count	Activated partial thromboplastin time b
International normalized ratio b	

<sup>a Can be recorded as absolute counts or as percentages.

For coagulation parameters, activated partial thromboplastin time and international normalized ratio are to be assessed at baseline on Day 1 (unless all screening laboratory hematology assessments are performed within 3 days prior to Day 1) and as clinically indicated.

#### Table 10 Urinalysis

Bilirubin	Ketones
Blood	pH
Color and appearance	Protein
Glucose	Specific gravity

Note: Urinalysis should be done at screening and then as clinically indicated.

Note: Microscopy should be used as appropriate to investigate white blood cells and use the high-power field for red and white blood cells.

If a patient shows an AST or ALT  $\ge 3 \times \text{ULN}$  together with total bilirubin  $\ge 2 \times \text{ULN}$ , refer to Appendix E for further instructions on cases of increases in liver biochemistry and evaluation of Hy's law. These cases should be reported as SAEs if, after evaluation, they meet the criteria for a Hy's law case or if any of the individual liver test parameters fulfill any of the SAE criteria.

All patients should have further chemistry profiles performed at 30 days ( $\pm 3$  days), 2 months ( $\pm 1$  week), and 3 months ( $\pm 1$  week) after permanent discontinuation of IP (see the SoAs).

Any clinically significant abnormal laboratory values should be repeated as clinically indicated and recorded on the eCRF. Situations in which laboratory safety results should be reported as AEs are described in Section 8.3.7.

All patients with Grade 3 or 4 laboratory values at the time of completion or discontinuation from IP must have further tests performed until the laboratory values have returned to Grade 1 or 2, unless these values are not likely to improve because of the underlying disease.

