## 8.3.8 **Hy's law**

Cases where a patient shows elevations in liver biochemistry may require further evaluation and occurrences of AST or ALT  $\ge 3 \times ULN$  together with total bilirubin  $\ge 2 \times ULN$  may need to be reported as SAEs. Please refer to Appendix E for further instruction on cases of increases in liver biochemistry and evaluation of Hy's law.

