## E 4.2 Potential Hy's law criteria met

If the patient does meet PHL criteria the Investigator will:

- Determine whether PHL criteria were met at any study visit prior to starting study treatment (See Section 8.4 Safety Reporting and Appendix E, Section 6. Actions Required When Potential Hy's Law Criteria are Met Before and After Starting Study Treatment)
- Notify the AstraZeneca representative who will then inform the central Study Team
- Within 1 day of PHL criteria being met, the Investigator will report the case as an SAE of Potential Hy's Law; serious criteria 'Important medical event' and causality assessment 'yes/related' according to CSP process for SAE reporting.

- For subjects that met PHL criteria prior to starting IMP, the investigator is not required to submit a PHL SAE unless there is a significant change# in the subject's condition
- The Study Physician contacts the Investigator, to provide guidance, discuss and agree an approach for the study patients' follow-up (including any further laboratory testing) and the continuous review of data.
- Subsequent to this contact the Investigator will:
  - Monitor the patient until liver biochemistry parameters and appropriate clinical symptoms and signs return to normal or baseline levels, or as long as medically indicated. Complete follow-up SAE Form as required.
  - Investigate the etiology of the event and perform diagnostic investigations as discussed with the Study Physician.
  - Complete the three Liver CRF Modules as information becomes available
    - # A 'significant' change in the subject's condition refers to a clinically relevant change in any of the individual liver biochemistry parameters (ALT, AST or total bilirubin) in isolation or in combination, or a clinically relevant change in associated symptoms. The determination of whether there has been a significant change will be at the discretion of the Investigator, this may be in consultation with the Study Physician if there is any uncertainty.

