# E 5 Review and assessment of potential Hy's law cases

The instructions in this section should be followed for all cases where PHL criteria are met.

As soon as possible after the biochemistry abnormality was initially detected, the Study Physician contacts the Investigator in order to review available data and agree on whether there is an alternative explanation for meeting PHL criteria other than DILI caused by the IP to ensure timely analysis and reporting to health authorities within 15 calendar days from date PHL criteria was met. The AstraZeneca Global Clinical Lead or equivalent and Global Safety Physician will also be involved in this review together with other patient matter experts as appropriate.

According to the outcome of the review and assessment, the Investigator will follow the instructions below.

If there is an agreed alternative explanation for the ALT or AST and TBL elevations, a determination of whether the alternative explanation is an AE will be made and subsequently whether the AE meets the criteria for a SAE:

• If the alternative explanation is **not** an AE, record the alternative explanation on the appropriate CRF

• If the alternative explanation is an AE/SAE, update the previously submitted Potential Hy's Law SAE and AE CRFs accordingly with the new information (reassessing event term; causality and seriousness criteria) following the AZ standard processes.

If it is agreed that there is **no** explanation that would explain the ALT or AST and TBL elevations other than the IP:

- Send updated SAE (report term 'Hy's Law') according to AstraZeneca standard processes.
  - The 'Medically Important' serious criterion should be used if no other serious criteria apply
  - As there is no alternative explanation for the HL case, a causality assessment of 'related' should be assigned.

If there is an unavoidable delay of over 15 calendar days in obtaining the information necessary to assess whether or not the case meets the criteria for HL, then it is assumed that there is no alternative explanation until such time as an informed decision can be made:

- Provides any further update to the previously submitted SAE of Potential Hy's Law, (report term now 'Hy's Law case') ensuring causality assessment is related to IMP and seriousness criteria is medically important, according to CSP process for SAE reporting.

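### Protocol 8.2.1 and Appendix E give different SAE triggers and deadlines for the same potential Hy's law laboratory finding

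*Protocol*

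**What the plan says.** The text below Table 10 in Protocol 8.2.1 takes a patient with AST or ALT at least 3 x ULN together with total bilirubin at least 2 x ULN and tells the site to "refer to Appendix E for further instructions on cases of increases in liver biochemistry and evaluation of Hy's law". The next sentence states a reporting rule of its own: "These cases should be reported as SAEs if, after evaluation, they meet the criteria for a Hy's law case". The same sentence then gives a second, alternative route to an SAE: "or if any of the individual liver test parameters fulfill any of the SAE criteria".

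Protocol 8.3.8 covers the same finding, says that such occurrences "may need to be reported as SAEs", and also points to Appendix E.

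Appendix E 2 defines potential Hy's law (PHL) by these laboratory thresholds alone, after the start of study medication. Hy's law needs the same thresholds and no explanation other than the investigational product. Appendix E 4.2 then sets the reporting rule: "Within 1 day of PHL criteria being met, the Investigator will report the case as an SAE of Potential Hy's Law". Seriousness is preset as an important medical event and causality as related. There is an exemption: "For subjects that met PHL criteria prior to starting IMP, the investigator is not required to submit a PHL SAE". It lapses if the patient's condition has changed significantly. E 6 and E 7 give comparable relief for criteria already met before treatment and for certain repeat episodes.

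Appendix E 5 describes the evaluation. The Study Physician contacts the investigator as soon as possible, "to ensure timely analysis and reporting to health authorities within 15 calendar days from date PHL criteria was met". Where the agreed explanation is itself an AE or SAE, the PHL report already submitted is updated. There is also a default for slow cases: "If there is an unavoidable delay of over 15 calendar days", E 5 presumes that no alternative explanation exists.

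**The concern.** One laboratory finding carries two reporting rules. In 8.2.1 the evaluation comes first and its result decides whether there is an SAE, apart from the individual-parameter route. In Appendix E the SAE comes first and the evaluation revises it. Neither text says which prevails.

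The introduction in E 1 adds to the ambiguity. It has the investigator report AEs and SAEs according to how the review turns out, so it reads more like 8.2.1 than like E 4.2.

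At stake is whether sites create the same safety record for the same liver case, and whether they create it at the same time. SAP 4.2.13.1 tabulates SAEs and treatment-related SAEs, and those tables start from what sites submit.

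**Working it through.** There is no sample size, power or alpha figure to reproduce. The check is a comparison of the texts, followed by tracing cases through each.

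**The rules side by side**

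| | 8.2.1 | 8.3.8 | Appendix E 4.2 and E 5 |
|---|---|---|---|
| Starting point | ALT/AST ≥3 x ULN with bilirubin ≥2 x ULN | same | same, on treatment |
| What makes it an SAE | evaluation meets Hy's law criteria, or one parameter meets an SAE criterion | left open | the laboratory criteria themselves |
| Place of the evaluation | before the report | not stated | after the report, as an update |
| Deadline | none of its own | none of its own | 1 day from criteria being met |

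Protocol 8.4.1 gives sites 24 hours from awareness of any SAE, but that does not close the gap. Under 8.2.1 the finding becomes an SAE only when one of its two routes is satisfied, so the 24 hours start from a different event.

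**Cases traced through both texts**

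1. *First on-treatment case, alternative explanation agreed, no individual parameter meets an SAE criterion.* 8.2.1: no Hy's law SAE. E 4.2: an SAE within 1 day, revised later under E 5. The texts differ on whether the case is submitted. Protocol 8.3.7 is unlikely to capture it by another route, because deterioration in a mandated laboratory value is reported only if it meets an SAE criterion or leads to discontinuation.
2. *First on-treatment case, no alternative explanation, no other SAE criterion.* 8.2.1: an SAE once the evaluation is complete. E 4.2: an SAE within 1 day. The texts differ on when. If an evaluation ran to the 15-calendar-day mark, the first SAE record would come 15 − 1 = 14 days later than under E 4.2, at the limit that E 5 sets for reporting to authorities. An evaluation finished sooner gives a smaller gap.
3. *An individual liver parameter meets an SAE criterion.* An SAE under both texts, so no conflict on whether to report.
4. *Criteria met before treatment, or a qualifying repeat episode, with no significant change.* Appendix E does not require a PHL SAE, so this case is outside the conflict.

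The conflict is therefore limited to cases 1 and 2.

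**Number of cases**

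The documents give no rate. As an assumption only, if 0.5% to 2% of 724 patients met the laboratory criteria, that would be 0.005 x 724 = 3.6 to 0.02 x 724 = 14.5 patients. This is a ceiling, because it includes cases 3 and 4 and all cases at sites that follow Appendix E.

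**The case against.** The best defence is the cross-reference. Both 8.2.1 and 8.3.8 send the site to Appendix E, which presents itself as the process for identifying and reporting Hy's law cases. A site that follows the reference reaches the 1-day rule before it reaches the evaluation. This lowers the practical risk but does not remove the conflict, because the sentence after the reference in 8.2.1 states a different rule and no order of precedence is given. The open wording of 8.3.8 can be squared with Appendix E, since exempt cases exist, but on its own it gives no trigger.

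Four stronger readings are tempting, and the documents do not support them:

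- *That 8.2.1 makes a case an SAE only on confirmation of Hy's law.* It has the second route through an individual parameter.
- *That E 5 grants the site at least 15 days.* It asks for contact as soon as possible. The 15 days are a limit for reporting to authorities, with a conservative presumption if information is still missing.
- *That the sponsor would not know of the case.* The evaluation is joint: E 1 has sponsor representatives take part, E 4.2 has the sponsor's representative notified, and E 5 has the Study Physician make contact. What may be late is the formal SAE record.
- *That the final SAE tables are shown to be distorted.* E 5 allows event term, causality and seriousness to be reassessed. Where the explanation is not an AE, it does not say what becomes of the SAE already submitted. The effect on final counts is possible but not established.

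The version history says that Appendix E was revised in Version 3.0 for a new process and lists only Appendix E as updated for that item. That 8.2.1 is carried-over text is a plausible inference and no more.

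**Conclusion.** The inconsistency is real and should be corrected. For first on-treatment cases that meet no other SAE criterion and are not exempt, the protocol gives two answers on whether a case with an alternative explanation is submitted as an SAE. It also gives two answers on when a confirmed case is first submitted: within 1 day, or after an evaluation to be done as soon as possible against a 15-calendar-day limit.

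The consequence is limited to the SAE record and its timing. PFS and OS are untouched. The potential Hy's law summary, narratives, plots and listings in SAP 4.2.13.2 are driven by laboratory values and do not depend on which rule a site followed. The number of cases affected cannot be taken from the documents. The conclusion rests on the wording alone and assumes nothing about how sites have in fact reported.

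**What to change.** Reconcile 8.2.1, 8.3.8 and the reporting sentence in E 1 with the rest of Appendix E, so that the protocol has one SAE trigger and one deadline for this finding. Replace the conditional sentence in 8.2.1 and the open wording in 8.3.8 with a plain statement that the Appendix E reporting rule applies, including its exemptions for criteria met before treatment and for repeat episodes (E 4.2, E 6 and E 7). A reference to E 4.2 alone would leave out part of that relief.

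Before database lock, compare the programmatic list of potential Hy's law cases from SAP 4.2.13.2 with the SAE database, and query every non-exempt case that has no SAE. Exempt cases should be marked first so that they do not generate needless queries.

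The cost is a wording change in three places, one reconciliation listing, and possibly a few additional SAE records that Appendix E already requires.
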